7.3 DATA MANAGEMENT SYSTEM

The eCRF database is provided by Software for Trials Europe (Berlin, Germany). It is stored on a dedicated server under the supervision of IPPMed in a professional hosting environment at Hetzner AG (Nürnberg, Germany).

7.4 DATA COLLECTION SCHEDULE

	Baseline	Intervention	Discharge	30 days	3/12 months
Demographics	x				
Comorbidities*	x				
Electrocardiogram (ECG)	x		x	x	x
Echocardiogram (TTE)	x		x	x	x
Echo Core Lab	x				
Risk Scores**	x			x	x
Procedural Data***		x			
Discharge Details			x		
Complications		x	x	x	x
Death Form			x	x	x
	
* Includes cardiovascular & cerebrovascular comorbidities, prior cardiac interventions and bicuspid valve disease
 
** Includes EuroSCORE II, STS and Frailty
 
*** Includes procedural and device-related information (delivery, success)
				

7.5 MONITORING

No monitoring visit is planned.

8 STATISTICAL ANALYSIS

8.1 SAMPLE SIZE DETERMINATION

Each site will recruit an average of 20 patients according to availability. A sample size of at least 60 patients in total is aimed for.

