1 SYNOPSIS

Title	The Circle Method Observational Project - Circle method for sizing and positioning in bicuspid valves
Background	
The bicuspid aortic valve (BAV) is the most common heart valve abnormality and is associated with a number of cardiac complications, including infective endocarditis, aortic dissection, aortic dilatation, and the development of severe aortic stenosis (AS). Due to its anatomical characteristics BAV has been considered a contraindication to transcatheter aortic valve implantation (TAVI), a standard treatment of AS. However, several recent trials have presented promising results indicating TAVI to be a safe alternative to surgery for low risk patients and more patients with BAV have been considered for TAVI.
 
There are several sizing techniques for TAVI in BAV, including an annular sizing, a supra-annular sizing, and a balloon sizing, yet there is still no consensus on the most appropriate technique. Although annular sizing remains the major approach in most patients with BAV, some BAV anatomies may profit from the supra-annular sizing. Recently published consensus for sizing and positioning the balloon-expandable Edwards SAPIEN 3 transcatheter heart valve (THV) in BAV describes the anatomical features that influence sizing optimization (1). The novel circle technique has also been proposed in the presence of the unique anatomical factors and sizing at the supra-annular level. This method is particularly helpful for visually identifying anatomic features, indicating the sealing zone at the commissures, visually reassuring of the size and position, and treating patients with large annuli. Currently, there are limited data validating the circle method for identifying sizing and positioning for TAVI in BAV patients.

Aim	To validate the circle method for sizing and positioning of SAPIEN 3 THV, using circles to simulate the SAPIEN 3 TAVI at 0, 3, 6, and 9 mm in 3mensio above and below the coronary arteries.
Trial design	Retrospective, non-interventional, 3mensio based analysis in 3 centers (Berlin, Katowice and Cambridge) and at least 60 eligible patients.

Patients	
Inclusion Criteria:
 
 • Patients with bicuspid aortic valves undergoing aortic valve replacement with a balloon expandable valve (SAPIEN 3 / Ultra) • Computed Tomography data available

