Primary objectives	
To assess whether patients with bicuspid aortic valves that received a SAPIEN 3 / Ultra THV suffered from fewer complications
 
 • if valve size was identical to the one determined using the circle method 
compared to
 
 • a case where circle method derived valve size is different from the actually implanted valve
Secondary objectives	
To develop recommendations on how to size the valve using the circle method.

Exploratory research questions / endpoints	
We aim to assess whether patients with bicuspid aortic valves that received a SAPIEN 3 / Ultra THV suffered from fewer complications
 
 • if valve size was identical to the one determined using the circle method 
compared to
 
 • a situation where circle method derived valve size is different from the actually implanted valve 
Complications are defined as:
 
 • Death • Stroke • Paravalvular Leakage (PVL) • Pacemaker implantations • Coronary occlusion • Malposition • Fistula to right ventricular outflow tract (RVOT) • Annulus rupture • Sinus sequestration • Valve embolisation
Schedule	
Baseline, Intervention, Discharge, 30 days, 3 months/12 months (according to availability, all retrospective)

Quality assurance / CoreLab	A CoreLab with the 3mensio Software and the most recent update as of January 2021 will be available to assess the CT data matching each patient. The two CoreLab physicians will independently assess the CT data based on the manual provided in the appendix. These data will be collated with the clinical dataset to assess correlations between measurements and complications / outcomes.
Statistics	No pre-specified statistical analyses, explorative approach.
Sample size	Given the limited data for sizing and positioning with the circle method in BAV patients, we aim to include at least 60 patients for this pilot study.

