Considering these anatomical variables, the circle technique has been suggested in cases of sizing optimization at the supra-annular level (1). This method includes a projection of an ellipse circle, which is one size smaller than the annulus size, in addition to the circle that is equivalent to the conventional sizing method. The technique is particularly helpful for visually identifying anatomic features, such as excessive calcified raphe, bulky leaflets, or eccentric calcifications in the aortic valvular complex, and preventing major vascular complications. Further advantages of the circle method include the indication of the sealing zone at the commissures, visual reassurance of the size and position, treatment of patients with large annuli, and its easy reproduction. However, as there are no strict thresholds on the sizing of the valve, physicians have to match the circle to the patient's BAV anatomy. The SAPIEN 3 THV has previously shown a good index of circularity, even in BAV (17). Therefore, projecting a circle through the aortic complex is the ideal approach for sizing as well as the positioning of the device. There is, however, limited data validation for the circle approach in patients with BAV.

In view of this, this project aims to validate the circle method for sizing and positioning of the device by evaluating the 30-day and 3-month outcomes of all consecutive patients with BAV undergoing TAVI.

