4 PARTICIPATING SITES

4.1 PARTICIPATING SITES

The project aims to collect data in three medical centers in Germany, Poland and the United Kingdom. A mean of 20 patients will be enrolled per site during a period of 6 months.

Site selection is based on the site's prior experience and patient availability.

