4.3 FEASIBILITY

The participating centers are departments of large academic, public or private hospitals. All centers have electronic medical records containing procedural perioperative data. All centers provide major surgery projects. Each center will have more than 20 eligible patients per year. This leads to an average number of at least 40 eligible patients who will be enrolled during the recruitment period in all centers. Therefore, including 40 patients into the project is realistic and feasible (expecting that about 60% of patients will give informed consent). All centers have experience in performing clinical research with patient-centered outcomes and guarantee feasibility of recruitment.

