5 PARTICIPATING PATIENTS

5.1 PATIENT POPULATION

A minimum of 60 patients in total (mean 20 per site) with BAV having TAVI surgery.

5.1.1 Inclusion Criteria:

1. Patients undergoing transcatheter aortic valve implantation (TAVI) with SAPIEN 3 / Ultra THV valve prosthesis
2. TAVI performed
3. 3mensio evaluation of Computed Tomography (CT) data

5.1.2 Exclusion criteria:

1. Surgical Aortic Valve Replacement
2. Pregnancy at the time of TAVI

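### The plan describes an all-consecutive cohort but sets no index-TAVI dates, consecutive-entry rule or screening log, so patients can be chosen with implanted size and outcome already known

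*Combined protocol and SAP*

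**What the plan says.** Section 2.1 closes by stating that the project validates the circle method by "evaluating the 30-day and 3-month outcomes of all consecutive patients with BAV undergoing TAVI". That is the only place where the cohort is called consecutive.

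The sections that decide who enters read as follows:

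- Synopsis, trial design: "Retrospective, non-interventional, 3mensio based analysis in 3 centers (Berlin, Katowice and Cambridge) and at least 60 eligible patients". The schedule row adds that follow-up data are "according to availability, all retrospective".
- Section 3.3: a recruitment period of 6 months, with follow-up at 30 days and 3 months.
- Section 4.1: "A mean of 20 patients will be enrolled per site during a period of 6 months".
- Section 4.3: "Each center will have more than 20 eligible patients per year", with about 60% expected to consent.
- Section 5.1.1: a SAPIEN 3 / Ultra implant, "TAVI performed", and a 3mensio evaluation of the CT. No dates are given.
- Section 8.1: "Each site will recruit an average of 20 patients according to availability", then "A sample size of at least 60 patients in total is aimed for".

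Section 9.3 requires written consent before data entry unless the local ethics body agrees otherwise. Section 7.5 plans no monitoring visit.

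**The concern.** A retrospective series is protected against selection by its sampling frame: fixed procedure dates, every case in that period screened, and a record of who was left out. Here the word consecutive appears in the background, and the operative sections contain none of the rules that would make it true. The only period given limits when a patient is entered, not when the valve was implanted.

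Because the TAVI has already been done, the implanted size and the early complications are normally on record when a site decides whom to approach. Entry that depends on outcome biases the complication rate. With no record of the patients not entered, the bias can be neither measured nor corrected afterwards. The primary objective in section 3.2.1 compares complications between patients whose implanted size was identical to the circle-method size and those whose size was different, so that comparison is exposed too if entry also tracks how well the size fitted.

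**Working it through.** **Inputs.** Three centers (synopsis, 4.1); mean 20 per site and minimum 60 in total (5.1, 8.1); more than 20 eligible per center per year, taken at its floor of 20, and about 60% consent (4.3); 6 months of entry (3.3, 4.1).

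**The plan's own figure.** 3 × 20 = 60. It reproduces.

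**Can the 6 months be the procedure window?** Eligible = centers × yearly rate × years = 3 × 20 × 0.5 = 30. Consented = 30 × 0.6 = 18, against 60. If consent were waived everywhere the figure is 30, still half the minimum.

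**Window implied by the target.** Patients to approach = 60 / 0.6 = 100. Months = 100 / (3 × rate) × 12.

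| Eligible per center per year | Months needed at 60% consent | Months needed if consent waived |
|---|---|---|
| 20 (stated floor) | 20 | 12 |
| 30 (assumed) | 13.3 | 8 |
| 40 (assumed) | 10 | 6 |
| 50 (assumed) | 8 | 4.8 |

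At 60% consent, 6 months of procedures would be enough only at 100 / (3 × 0.5) = about 67 eligible per center per year. The protocol gives only a lower bound, so the length of the look-back is undetermined. At or near that bound it is well beyond 6 months.

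**Effect of outcome-dependent entry (all values assumed; no true difference).** Let p be the true complication rate and d the fraction by which complicated cases are entered less often than others. The observed rate is p(1 − d) / (1 − pd). With p = 20%:

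- d = 10%: 0.18 / 0.98 = 18.4%
- d = 25%: 0.15 / 0.95 = 15.8%
- d = 50%: 0.10 / 0.90 = 11.1%

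The odds become (1 − d) times the true odds whatever p is. With under-entry d1 in the identical-size group and d2 in the different-size group, the expected odds ratio under no effect is (1 − d1) / (1 − d2):

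- d2 = 0 and d1 = 10%, 25% or 50%: odds ratio 0.90, 0.75 or 0.50
- d1 = d2: odds ratio 1.0, although both observed rates are too low

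**The case against.** Several points on the other side are sound and limit what can be claimed.

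- *A reader might infer that each site has about 40 candidates for 20 places.* The documents do not support that. Twenty is a mean and 60 a minimum; neither is a cap, and a site may enter everyone. Two years at the floor gives 40 eligible but 40 × 0.6 = 24 consented, so the surplus at the stated rates is small. Choice remains over whom to approach and how far back to go.
- *A reader might infer that the availability wording in 8.1 contradicts section 2.1.* Beside an average, it more naturally means that site totals vary with volume. The operative text is silent on consecutiveness; it does not set a conflicting rule.
- *A reader might take the odds ratio of 0.50 as the expected bias.* It requires halved entry of complicated cases in the matched group alone. Two core lab physicians assess the CT data (synopsis, CoreLab row), so the study's match status is not formally known at entry. Knowing the outcome alone would tend to give similar under-entry in both groups and an odds ratio near 1.0. A site does hold the CT, and section 2.1 calls the method easy to reproduce, so differential entry is possible but conditional.
- *A reader might infer that a patient implanted just before entry could never supply the 3-month outcome.* Sections 3.3 and 3.4 allow follow-up to mature before the project closes. That sits awkwardly with the all-retrospective schedule in the synopsis, but it does not show that outcomes would be missing.
- The project is a pilot with an exploratory analysis. That lowers the standard for formal inference. It does not remove selection bias, and sections 3.2.1 and 3.2.2 still aim to validate the method and to develop sizing recommendations.

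**Conclusion.** The point stands in limited form. The consecutive cohort described in section 2.1 is not secured by any eligibility, timeline or sample-size rule. At or near the stated floor, sites must look back over an unspecified period, about 20 months at the floor itself, and can decide whom to approach with implanted size and outcome known. This rests on the floor of 20 per center per year and 60% consent; higher volumes shorten the look-back but do not supply the missing dates.

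The direct risk is to the complication rate: on assumed figures, a true 20% could appear as anything from 18.4% down to 11.1%. Distortion of the identical-versus-different contrast needs the further condition that entry depends on size match; on that assumption the odds ratio would lie between 0.90 and 0.50 with no true effect. The documents do not show that sites will select in this way, only that nothing prevents it or would reveal it. The difference between the totals of 40 (3.1, 4.3) and 60 (5.1, 8.1) is a separate matter.

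**What to change.** In 5.1.1, state a first and last index-TAVI date for each site, fixed before screening starts. Put the last date at least 3 months before data entry, so that the 3-month outcome can exist; this also fits the all-retrospective schedule. Make the window long enough to reach at least 60 patients after expected non-consent, which means about 100 eligible patients at 60% consent.

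Within the window, screen every BAV patient who received a SAPIEN 3 / Ultra. Enter all who are eligible and either consent or are covered by an ethics exception, without stopping at 20. Keep a log giving the reason for each non-entry: no CT, refusal, death, or excluded. Recording death matters because it is a listed complication and a patient who has died cannot sign.

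Replace the availability wording in 8.1 with this rule, and report the log so that readers can check how close the series comes to consecutive. The log will not recover the roughly 40% expected not to consent, but it will show how many were lost and why.

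The cost is protocol wording and site time to build the log from existing procedure lists. Final site numbers would be set by the window instead of by a target. No procedures are added.

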8.2 DESCRIPTIVE ANALYSIS

Statistical analysis will be performed for the total study population. Continuous variables will be presented as mean \pm SD or as median with interquartile range, and categorical variables (e.g. gender) will be reported as frequencies and percentages. The Kolmogorov-Smirnov test will be used to test for normal distribution. For comparisons, Chi-Square or Fisher exact test will be used for categorical variables, and Student's t-test or Mann-Whitney U for continuous variables.

All statistical analyses will be performed using IBM SPSS Statistics version 29 (IBM, Armonk, New York) or R Core Team (<https://www.R-project.org/>).

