6 DOCUMENTATION

6.1 STANDARD EXAMINATIONS

The clinical outcome data collected and entered should be based on the site standards of care for aortic valve replacement. The collected data include medical history, physical assessments, safety parameters, ECG, laboratory results, and transthoracic / transesophageal echocardiography.

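### Section 8.2 compares complications as crude proportions and gives no denominator for patients without a follow-up record, although post-discharge follow-up is whatever routine care produced

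*Combined protocol and SAP*

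**What the plan says.** - **Analysis (Section 8.2).** "Statistical analysis will be performed for the total study population", and "categorical variables (e.g. gender) will be reported as frequencies and percentages". Group comparisons of categorical variables use Chi-square or Fisher tests. The section gives no denominator for a visit, no rule for missing follow-up, no minimum follow-up and no time-to-event method. No other section supplies one.
- **Comparison (Synopsis, primary objectives; Section 3.2.1).** Complications when the implanted size equals the circle-method size are compared with "a case where circle method derived valve size is different from the actually implanted valve". Below these are called the matched and mismatched groups.
- **Follow-up (Synopsis, Schedule).** The last visit is given as "3 months/12 months (according to availability, all retrospective". The end of Section 2.1 and Section 3.3 name only 30 days and 3 months. Section 7.4 has a single column for 3/12 months.
- **Source of outcomes (Section 6.1).** Outcome data "should be based on the site standards of care for aortic valve replacement". There are three centres in three countries (Section 4.1).
- **Verification (Section 7.5).** "No monitoring visit is planned".

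**The concern.** A proportion test needs every patient to be classified as with or without the event over the same period. Here the period differs between patients: one may be documented to discharge, another to 30 days, another to 12 months. The test in Section 8.2 has no place for partial follow-up, so whoever runs the analysis must choose between two treatments that the plan does not mention.

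- **Count patients without a record as event-free.** Every post-discharge risk is understated. If records are more complete in one group, the primary comparison partly measures record-keeping. One route would be an uneven spread of matched and mismatched patients over centres with different follow-up routines.
- **Drop patients without a record.** The time for which they were observed is discarded, and those left are the patients who came back, which may depend on having had a problem.

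Because the plan names neither, the choice can be made after the results are known.

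**Working it through.** **The plan's own figure.** The sample size is site arithmetic: 3 centres × mean 20 = 60, which agrees with Section 8.1. No significance level, power, effect size or dropout is given, so there is no power calculation to reproduce.

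**Inputs, all assumed.** The same true risk p in both groups (10% to 40%); records exist for a share c1 of one group and c2 of the other, unrelated to outcome; two groups of 30; two-sided 5% level.

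**Treatment 1: no record counted as event-free.** The expected observed risks are p × c1 and p × c2, so the false difference is p × (c1 − c2). This does not depend on group size. The probability of a significant result was obtained by exact binomial enumeration for 30 v 30 (Chi-square without continuity correction).

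| True risk in both groups | Capture | Observed risks | False difference (points) | Significant, Chi-square | Significant, Fisher |
|---|---|---|---|---|---|
| 10% | 95% v 80% | 9.5% v 8.0% | 1.5 | 5.6% | 0.8% |
| 10% | 100% v 60% | 10.0% v 6.0% | 4.0 | 8.5% | 1.5% |
| 20% | 90% v 70% | 18.0% v 14.0% | 4.0 | 7.2% | 2.9% |
| 30% | 95% v 80% | 28.5% v 24.0% | 4.5 | 6.7% | 3.7% |
| 30% | 90% v 70% | 27.0% v 21.0% | 6.0 | 8.2% | 4.6% |
| 30% | 100% v 60% | 30.0% v 18.0% | 12.0 | 18.9% | 12.2% |
| 40% | 100% v 60% | 40.0% v 24.0% | 16.0 | 25.8% | 18.3% |

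Over all four risks (10%, 20%, 30%, 40%) and the three unequal capture patterns, the false difference runs from 1.5 to 16 points and the Chi-square rejection rate from 5.6% to 25.8%. With equal capture of 90% there is no false difference, but a true 30% is reported as 0.30 × 0.90 = 27%.

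**Treatment 2: only patients with a record.** If missing records are unrelated to outcome, both groups have expected proportion p and the false difference is zero. The Chi-square rejection rate is then 3.3% to 5.9% over the same risks and all capture patterns tried. If missing records depend on outcome, the bias stays. As an illustration, take p = 30% and suppose all patients with an event have a record but only 60% of those without one do. The proportion among patients with a record is then 0.30 / (0.30 + 0.70 × 0.60) = 0.30 / 0.72 = 41.7%.

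Neither treatment is safe without further information, and neither uses the follow-up time actually observed.

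**The case against.** **The text does not say that unrecorded patients are event-free.** A reader might infer from "Statistical analysis will be performed for the total study population" that every percentage is taken over all enrolled patients and that a missing record means no complication. The sentence only names who is analysed; a denominator of patients with a record fits it equally well. This objection stands. The figures for treatment 1 are therefore conditional and are not results that the plan prescribes.

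**Unequal capture is not documented.** Circle-method sizing is done by two core-lab physicians from CT, so there is no direct route from agreement status to a site's follow-up routine. This also stands. Imbalance across centres is possible, but the documents give no figures for it.

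**Many complications are procedural or in-hospital.** Annulus rupture, coronary occlusion and valve embolisation, for example, would usually be recorded at intervention or discharge, and Section 4.3 says all centres hold electronic perioperative data. This narrows the point to later death, stroke, pacemaker implantation and PVL. The availability bracket in the Synopsis follows the 3- and 12-month visits and may not cover 30 days; for that visit the point rests on Section 6.1.

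**Written consent limits complete loss.** Sections 7.2 and 9.3 require it before data entry, unless a local committee agrees otherwise, so most patients will have been reached. This makes a patient never heard of again less typical, but contact for consent is not a record of outcomes at each visit.

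**Test inflation is often modest, and the work is exploratory.** At 30% risk with 90% v 70% capture, Fisher rejects 4.6% of the time. True, but the 6-point bias in the estimate remains, and an exploratory study is read mainly through its estimates.

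**Conclusion.** The point holds in limited form. For post-discharge complications the plan pairs a crude proportion test with follow-up of unequal and unspecified length, and states neither the denominator nor how patients without a record are handled. If they are counted as event-free, risks are understated and unequal capture produces a false difference of about 1.5 to 16 points, under assumed true risks of 10% to 40% and capture from 95% v 80% to 100% v 60%. The main harm is biased estimates; false significance is secondary except at the widest capture gaps. If such patients are dropped, partial follow-up is lost and bias remains whenever returning depends on outcome.

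The documents do not support the stronger conclusions that the plan will count missing records as complication-free, or that capture differs between the matched and mismatched groups. Procedural and in-hospital complications are little affected. The change should be made, because the gap bears on the primary comparison and is cheap to close.

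**What to change.** Amend Section 8.2 as follows.

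1. Keep proportions with Chi-square or Fisher tests for procedural and in-hospital complications.
2. For post-discharge death, stroke and pacemaker implantation, use time from TAVI to the event, censored at last documented contact. Report Kaplan-Meier risks at 30 days and 3 months, and at 12 months where available, with a log-rank comparison of the two groups.
3. Use patients with a post-implant echocardiogram as the denominator for PVL.
4. Show the number of patients with a record at each visit, by agreement group.
5. Add a best/worst-case sensitivity analysis for patients without a record.
6. Record event date and last-contact date in the eCRF. Section 7.4 lists complication and death forms but no date fields, so it should be confirmed that sites can supply both.

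**Cost.** Two date fields, a standard analysis and wider intervals at late time points. Censoring at last contact assumes that those lost have the same later risk as those still followed. If patients return because of a problem, this fails and Kaplan-Meier does not repair it, which is why items 4 and 5 are needed.

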3 PROJECT DESIGN & OBJECTIVES

3.1 PROJECT DESIGN

This is a non-interventional, retrospective, multicenter, international project. A minimum of 40 patients in Germany and Poland will be enrolled in the project by contributing sites during the enrollment period.

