3.2 PROJECT OBJECTIVES

3.2.1 Primary Objective

The primary objective of this project is to validate the circle method for sizing and positioning of the SAPIEN 3 THV in patients with BAV. In particular we aim to assess whether patients with BAV that received a SAPIEN 3 / Ultra THV suffered from fewer complications if valve size was *identical* to the one determined using the circle method compared to a situation where circle method derived valve size is *different* from the actually implanted valve.

We will use circles to simulate the SAPIEN 3 THV at 0, 3, 6, and 9 mm in 3mensio above and below the coronary arteries.

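### Section 8.2 names Student's t-test for groups whose sizes the data determine; Welch's t-test would hold the 5% level if sizes and SDs both differ, and the Kolmogorov-Smirnov check cannot detect that problem

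*Combined protocol and SAP*

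**What the plan says.** Section 8.2 (Descriptive analysis) lists a normality check, "The Kolmogorov-Smirnov test will be used to test for normal distribution", and then the comparison tests: "Chi-Square or Fisher exact test will be used for categorical variables", and "Student's t-test or Mann-Whitney U for continuous variables". It does not say that the normality result selects the test, although no other purpose for the check is evident. It does not say whether the check is run per group or on pooled data, or with the Lilliefors correction. Neither Welch's test nor a check of variances is mentioned, and the software may be SPSS or R.

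Two kinds of grouping are in view. Section 3.2.1 contrasts patients whose implanted size matched the circle method, "compared to a situation where circle method derived valve size is *different* from the actually implanted valve". The synopsis, under Quality assurance / CoreLab, says of the CT measurements: "These data will be collated with the clinical dataset to assess correlations between measurements and complications / outcomes". On size, section 8.1 says "A sample size of at least 60 patients in total is aimed for", while section 3.1 says "A minimum of 40 patients in Germany and Poland will be enrolled in the project by contributing sites during the enrollment period". On status, the synopsis says "No pre-specified statistical analyses, explorative approach".

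**The concern.** Student's t-test pools the two group variances. When one group is both smaller and more variable, the pooled figure understates the variance of the difference in means and the test rejects too often. When the larger group is the more variable one, it rejects too rarely. The plan does not fix the group sizes: agreement between implanted and circle-derived size is observed afterwards, and so is the occurrence of complications. An uneven split is therefore plausible, and some listed complications may leave one group small (an assumption, since no rates are given).

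The only screening step in section 8.2 concerns the shape of the distribution, so unequal variances would pass through it. At stake are the exploratory comparisons of continuous measurements, such as CT dimensions, between these groups. A nominal 5% p-value there could stand for a rate well above or below 5%.

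**Working it through.** The plan states no alpha, power, SD or group split, so it has no figure to reproduce. The total of 60 comes from section 8.1. A total of 40 (section 3.1) is a sensitivity case. The two-sided 5% level, the splits, the SD ratios and the distribution shapes are assumptions.

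**1. Student's t-test, approximate calculation.** With group sizes n1, n2 and SDs s1, s2:

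- True variance of the difference: V = s1²/n1 + s2²/n2.
- Variance that the test uses, on average: P = [((n1−1)s1² + (n2−1)s2²)/(n1+n2−2)] × (1/n1 + 1/n2).
- The test in effect compares a standard normal value with c = t(0.975, n1+n2−2) × √(P/V).

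For n1 = 45, s1 = 1, n2 = 15, s2 = 2:

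- V = 1/45 + 4/15 = 0.289.
- P = [(44 + 56)/58] × (1/45 + 1/15) = 1.724 × 0.0889 = 0.153.
- c = 2.002 × √(0.153/0.289) = 2.002 × 0.728 = 1.458, so the two-sided rejection rate is about 14.5%.

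With the SDs reversed (s1 = 2, s2 = 1):

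- V = 4/45 + 1/15 = 0.156.
- P = [(176 + 14)/58] × 0.0889 = 0.291.
- c = 2.002 × 1.368 = 2.739, or about 0.6%.

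The normal approximation reads slightly low: it gives 4.5% where the true rate is 5%.

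**2. Simulation on normal data with equal means, 50,000 runs per setting.**

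| Split | SD ratio | Student, smaller group more variable | Student, larger group more variable | Welch |
|---|---|---|---|---|
| 30/30 | up to 2 | 0.049–0.052 (groups equal) | 0.049–0.052 (groups equal) | 0.048–0.052 |
| 40/20 | 1.5 | 0.085 | 0.026 | 0.050–0.051 |
| 40/20 | 2 | 0.111 | 0.017 | 0.048–0.051 |
| 45/15 | 1 | 0.049–0.050 (SDs equal) | 0.049–0.050 (SDs equal) | 0.051 |
| 45/15 | 1.5 | 0.106 | 0.018 | 0.049 |
| 45/15 | 2 | 0.153 | 0.009 | 0.049–0.051 |
| 30/10 (total 40) | 2 | 0.155 | 0.009 | 0.050–0.052 |

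A separate run of 100,000 per setting at 45/15 agreed: Student 0.108 and 0.153 with the smaller group more variable, 0.017 and 0.008 with the larger, and Welch 0.048–0.050.

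**3. Does the normality check help?** The two-step procedure was Kolmogorov-Smirnov (Lilliefors) per group, then t or Mann-Whitney U. At SD ratio 2 with the smaller group more variable it gave 0.112 (40/20) and 0.151 (45/15), practically the same as Student's t alone. Mann-Whitney alone gave 0.085 and 0.101, so it is not a remedy for unequal spread.

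**4. How sensitive is the check to non-normality?** Rejection rates at the 5% level:

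| Distribution | n | KS, uncorrected | KS, Lilliefors | Shapiro-Wilk |
|---|---|---|---|---|
| Gamma, skewness 1 | 20 | 0.003 | 0.19 | 0.30 |
| Gamma, skewness 1 | 60 | 0.03 | 0.47 | 0.78 |
| Lognormal, sigma 0.5 | 20 | 0.015 | 0.35 | 0.51 |
| Lognormal, sigma 0.5 | 60 | 0.17 | 0.78 | 0.96 |
| Exponential | 30 | 0.12 | 0.78 | 0.97 |
| Exponential | 60 | 0.53 | 0.99 | 1.00 |

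Shapiro-Wilk is the stronger test in every row. Which Kolmogorov-Smirnov version is run changes the result greatly, and section 8.2 does not name one.

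**5. Price of Welch when variances are equal.** At 45/15 and a true difference of 0.9 SD (100,000 runs), power falls from 84% to 82%. At 52/8 it falls from 64% to 57%.

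**The case against.** The strongest reply is that little depends on this. The primary comparison concerns complications such as death, stroke and pacemaker implantation, which go to Chi-square or Fisher. The analysis is labelled exploratory, and section 8.2 is titled as descriptive. No passage says that t-test p-values will decide the sizing recommendations of section 3.2.2. The t-test fault also needs unequal sizes and unequal SDs together, and the documents give neither. All of this stands, and it sets the severity.

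A reader might also infer stronger claims that the documents do not support:

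- **That comparing a small group with a large one breaks Student's t by itself.** It does not. At 45/15 with equal SDs the level is 0.049–0.050.
- **That Kolmogorov-Smirnov almost never rejects at this size.** This is true of the uncorrected version at small n or with mild skew. With the Lilliefors correction at n = 60 it detects strong skew in 78% to 99% of samples.
- **That skewed data would pass the check and cost a great deal of power.** For lognormal data with sigma 1, at 30/30, forcing the t-test gives about 63% against 78% for Mann-Whitney. If the check does select the test, such data mostly go to Mann-Whitney and the two-step power is also 78%. At 20/40 the two-step procedure gives about 70% to 75%, depending on the version and how it is applied, against 74% to 75% for Mann-Whitney alone.
- **That a weak normality check inflates false positives.** With the same skewed distribution in both groups, the two-step procedure (Lilliefors) stayed at 0.045–0.054.

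So the choice of normality test and the choice of t-test are separate matters, and a more powerful normality test would not repair the second.

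**Conclusion.** The point holds in a limited form and is minor. For continuous variables, section 8.2 names a test whose level depends on equal group sizes or equal variances, in a project that controls neither. Under an assumed 15 versus 45 split, type I error is about 11% to 15% with the smaller group 1.5 to 2 times as variable, and about 2% to 1% in the reverse case. Welch's test stays near 5% throughout on normal data. The Kolmogorov-Smirnov step gives no protection, is weaker than Shapiro-Wilk, and is not specified closely enough to be reproduced. That it selects the test is a natural reading, not a written rule.

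The size of the effect rests wholly on assumed splits and SD ratios. If the groups turn out similar in size or in spread, Student's t is sound. Nothing here bears on the primary comparison of complications.

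**What to change.** In section 8.2:

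1. Replace Student's t-test with Welch's t-test.
2. Replace the Kolmogorov-Smirnov pre-test with a statement, made before analysis, of which continuous variables will be compared by Welch's test (roughly symmetric) and which by Mann-Whitney U (skewed). If a check of shape is kept, use Q-Q plots or Shapiro-Wilk.

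This takes two sentences and no extra data, and both tests are available in the named software. The costs are small but real. If variances are equal, Welch loses one or two percentage points of power at 15 versus 45, and more with very small groups. Neither test is exact everywhere. With exponential data in both groups Welch gave 0.060 at 45/15 and 0.077 at 50/10, and Mann-Whitney drifts from 5% when spreads differ. Where a complication group is very small, reporting the estimate with its confidence interval will say more than the p-value.
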